7.3.1.3 Disease Activity Score-C-Reactive Protein (DAS28-hsCRP)

The DAS28-hsCRP is a measure of disease activity in 28 joints that consists of a composite numerical score of the following variables: TJC, SJC, hsCRP, and Subject's Global Assessment of Disease Activity (21).

For DAS28-hsCRP, the 28 joints to be examined and assessed as tender or not tender for TJC and to be examined and assessed as swollen or not swollen for SJC include 14 joints on each side of the subject's body: 2 shoulders, 2 elbows, 2 wrists, 10 metacarpophalangeal joints, 2 interphalangeal joints of the thumb, 8 proximal interphalangeal joints, and 2 knees (22).

DAS28-hsCRP will be derived using the following formula from the DAS28 website (23):

$$DAS28-hsCRP = 0.56*\sqrt{(TJC28)} + 0.28*\sqrt{(SJC28)} + 0.014*GH + 0.36*ln(hsCRP+1) + 0.96$$

Where:

- TJC28=28 joint count for tenderness
- SJC28=28 joint count for swelling
- ln(hsCRP)=natural logarithm of hsCRP
- GH=the general health component of the DAS (ie, patient's global assessment of disease activity).

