13.3 Other Baseline Characteristics

13.3.1 Disease history

Information on RA baseline disease characteristics collected during screening will only be summarized for the primary analysis.

Information on RA baseline disease characteristics collected during screening will be summarized in total and by treatment arm. Descriptive statistics will be presented for:

- Time (months) since confirmed diagnosis of RA according to 2010 ACR/The EULAR RA classification criteria. Time will be computed as $(\text{Date of Informed Consent Signature} - \text{Date of confirmed diagnosis of RA}) / 30.4375$. If the date of confirmed diagnosis of RA is entirely missing, then time since confirmed diagnosis of RA will not be computed. In case of partial missing date of confirmed diagnosis of RA, this date will be imputed as follows:
 - If only the day is missing, then it will be replaced by the first day of the month
 - If both day and month are missing, then it will be replaced by the first of January
- The count of Tender Joint Count 68 (TJC68)
- The count of Swollen Joint Count 66 (SJC66)

- Physician's Global Assessment of Disease Activity using horizontal Visual Analog Scale (VAS) in mm
- Subject's Global Assessment of Disease Activity using horizontal VAS in mm
- Subject's Assessment of Pain using horizontal VAS in mm
- Subject's Assessment of Physical Function as measured by HAQ-DI will be derived ([Appendix 1: HAQ-DI scoring](#)) and described overall and by dimensions (dressing and grooming, getting up, eating, walking, hygiene, reach, grip, activities)
- hsCRP (mg/L) as a continuous variable and by category (normal/high based on central normal laboratory ranges)
- ESR (mm/Hr) as a continuous variable and by category (low/normal/high based on local normal ranges collected in eCRF)
- Acute-phase reactant (at least one test result is needed for the classification): normal hsCRP and normal ESR, abnormal hsCRP or abnormal ESR. Abnormal refers to either low or high normal range classification.
- RF (expressed in kU/L) as a continuous variable and classified as negative (\leq Upper Limit of Normal [ULN]) and positive ($>$ ULN)
- Anti-CCP antibodies classified as a continuous variable and as negative (\leq ULN) and positive ($>$ ULN)
- Serology (at least one test result is needed for the classification): negative RF and negative anti-CCP (\leq ULN), low-positive RF or low-positive anti-CCP ($>$ ULN, $\leq 3*ULN$), high-positive RF or high positive anti-CCP ($>$ $3*ULN$)

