Primary analysis	mITT Analysis Set	12-Week treatment period until start of OLE or discontinuation of treatment prior to OLE, whichever is applicable	Placebo or M2951 50 mg BID	All data collected during the 12-Week treatment period up to start of OLE if applicable
Final analysis	OLE mITT Analysis set	OLE period only	Placebo/M2951 50 mg BID only	Data from OLE period only, or posterior to OLE (Safety follow-up / End of Study)
		Both 12-Week treatment period and OLE period	M2951 50 mg BID/M2951 50 mg BID only	Data from both periods (12-Week treatment and OLE period), ie all data collected throughout the study

The Table 12 summarizes the analyses of efficacy endpoints:

Table 12 : Summary of efficacy endpoints for the primary analysis

Analysis	Endpoint	Method	Missing Data Handling
Primary endpoint	ACR20 at Week 12/Day 84	(1) Primary: Computation of response rate, point estimate and 2-sided 80% CI for Δ based on the “corrected Miettinen-Nurminen” method (2) Supportive**: logistic regression with treatment and baseline hsCRP as covariates	Primary: LOCF-NR (Table 3) Sensitivity: See Table 13
Key secondary endpoint	hsCRP CFB at Week 4/Day 28 and Week 12/Day 84	(1) Primary: ANCOVA model (2) Supportive: Hodges-Lehmann estimation for 80% CI	Primary: LOCF

Analysis	Endpoint	Method	Missing Data Handling
Other secondary endpoints	ACR20 response at each visit	(1) Primary: Computation of response rate, point estimate and 2-sided 80% CI for Δ based on the “corrected Miettinen-Nurminen” method (2) Supportive: logistic regression with treatment and baseline hsCRP as covariates	Primary: LOCF-NR (Table 3) Sensitivity: See Table 13
	ACR50/ACR70 response at each visit	(1) Primary: Computation of response rate, point estimate and 2-sided 80% CI for Δ based on the “corrected Miettinen-Nurminen” method (2) Supportive: logistic regression with treatment and baseline hsCRP as covariate	Primary: LOCF-NR (Table 3) Sensitivity: See Table 13
	CFB and percent CFB at each visit for each ACR component, ESR, anti-CCP, RF	Summary Statistics	As observed
	CFB in DAS28-hsCRP score at Week 4/Day 28, and Week 12/Day 84	(1) Primary : ANCOVA model (2) Supportive: Hodges-Lehmann estimation for 80% CI and ANCOVA model with baseline hsCRP as covariate	Primary: LOCF of each component prior to DAS28 calculation

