	Percentage of subjects with DAS28-hsCRP < 3.2 (well-controlled disease) at Week 12/Day 84	(1) Primary: Computation of response rate, point estimate and 2-sided 80% CI for Δ based on the “corrected Miettinen-Nurminen” method (2) Supportive: logistic regression with treatment and baseline hsCRP as covariate	Primary: LOCF-NR (Table 3)
	Percentage of subjects with DAS28-hsCRP < 2.6 at Week 12 / Day 84	(1) Primary: Computation of response rate, point estimate and 2-sided 80% CI for Δ based on the “corrected Miettinen-Nurminen” method (2) Supportive: logistic regression with treatment and baseline hsCRP as covariate	Primary: LOCF-NR (Table 3)
** All supportive analysis will be based on the primary missing data imputation method. No sensitivity analysis of missing data imputation will be performed for all supportive analyses.			

The Table 13 summarizes the sensitivity analyses to be performed on missing data imputations:

Table 13 : Sensitivity analysis for the primary analysis

Endpoint	Method
ACR Response	
Non-responder imputation (NR): ACR20 response rate will be evaluated on mITT analysis set. Subjects with missing ACR score will be considered as non-responders.

	
Completely Missing at Random pattern (MCAR): ACR20 response rate will be evaluated as observed without any LOCF imputation on mITT analysis set.

	
Missing At Random pattern (MAR): ACR20 will be imputed using multiple imputations process using MI SAS procedure as follows:
 
 1. Monotone missing data structure will be created as follows: intermediate (non-monotone) missing data will be multiply imputed using the Markov chain Monte Carlo (MCMC) method and assuming MAR and multivariate normality. Transformation of data will only be used if there is a clear deviation from normality. The SAS procedure PROC MI with the MCMC option will be used with seed number=20170524. The number of burn-in iterations will be set to 200, which is the default value. Nevertheless, if diagnosis plots show that the convergence has not yet occurred, this will be adjusted. 2. Then, each component will be imputed with treatment group, hsCRP at baseline and data at previous visit from all ACR20 components as covariates. 3. Imputation will be repeated 1000 times. The ACR20 will then be calculated for each of the multiply imputed data sets from the imputed components. Results will be combined using MIANALYZE SAS procedure with the Rubin's rules.

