16.2 Secondary Endpoint Analyses

16.2.1 Key secondary endpoint analysis

The key secondary endpoint is the change in hsCRP from Baseline to Week 4 and will be presented on the mITT Analysis Set.

Descriptive statistics will be presented by treatment group for CFB as well as percent CFB of hsCRP. A point estimate and 2-sided 80% CI for the difference Δ in Week 4 hsCRP mean CFB between subjects treated with M2951 + MTX and subjects treated with placebo + MTX (reference) will be provided.

Point estimate and its CI limits will be estimated with SAS® GLM procedure using LSMEANS statement. The ANCOVA will include baseline as a covariate and treatment group as an independent variable. A sensitivity analysis will be performed using a non-parametric method. The Hodges-Lehmann difference median estimate and 80% CI will be calculated with SAS® NPAR1WAY procedure using HL statement. Asymptotic and exact CIs will be computed.

Assumptions for the ANCOVA models:

Validity of the model will be verified as follows:

- The homogeneity of variances between treatment groups will be checked using the Levene's test. A scatter plot of residuals versus fitted values will be also performed.
- In order to assess the independence of error terms, a residual lag plot will be performed, ie constructed by plotting residual (i) against residual (i-1).
- A scatter plot of the response variable against the covariate, using separate symbols for each treatment group will be performed to verify the presence of linear relationship between the covariate and the response variable, and that all treatment regression lines have the same slope.
- Homogeneity of regression slopes will be verified by first running the model with the interaction between the covariate and the treatment group. This assumption will be validated if this interaction is not significant. If this assumption is verified, then the interaction will be removed from the model.
- Normality of residuals will be checked by computing Skewness and Kurtosis, which should fall within the interval [-2;2]. Normal QQ-plot of residuals will be performed as well.

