16.2.2 Other secondary endpoint analyses

The following efficacy endpoint analyses will be performed for the primary analysis and presented on the mITT Analysis Set:

- ACR20 response at each visit
- ACR50/ACR70 response at each visit
- Change and percent change in hsCRP from Baseline to Week 12
- CFB in DAS28-hsCRP score at Week 4 and Week 12
- Percentage of subjects with DAS28-hsCRP < 3.2 (well-controlled disease) at Week 12
- Percentage of subjects with DAS28-hsCRP < 2.6 at Week 12
- CFB in ESR, anti-CCP, RF (at Week 4 and Week 12)
- CFB to Week 12 in subject's self-assessments including:
 - Global assessment of disease activity (VAS)
 - Self-assessment of pain (VAS)
 - Self-assessment of disability (HAQ-DI)
- CFB to Week 12 in Physician's Global Assessment of Disease Activity (VAS).

The Week 12 hsCRP CFB will be analyzed in the same way as the Week 4 hsCRP CFB, ie descriptive statistics, ANCOVA model and sensitivity analysis using Hodges-Lehmann difference median estimate and 80% CI. This analysis will also be applied to DAS28-hsCRP score CFB at Week 4 and Week 12. The DAS28-hsCRP will be derived using the formula presented in [Appendix 2](#).

ACR50 and ACR70 are defined in the same way as the ACR20 using at least 50% and 70% improvement, respectively. The ACR50 and ACR70 proportions will be analyzed in the same way as the Week 12 ACR20 proportions.

This analysis will also be applied to Week 12 "DAS28-hsCRP < 3.2" proportion and Week 12 "DAS28-hsCRP < 2.6" proportion, but without the sensitivity analysis.

Proportions of ACR20/50/70, "DAS28-hsCRP < 3.2" and "DAS28-hsCRP < 2.6" will also be presented by treatment group and time point as observed, ie without any imputation.

Descriptive statistics

Descriptive statistics will be tabulated by treatment group and time point for the following continuous variables, both absolute value and CFB. The summary statistics will be provided as observed without imputation of missing data.

- DAS28-hsCRP score
- hsCRP (CFB and percent CFB)
- ESR
- anti-CCP
- RF

- TJC68 (CFB and percent CFB)
- SJC66 (CFB and percent CFB)
- subject's global assessment of disease activity (CFB and percent CFB)
- subject's assessment of pain (CFB and percent CFB)
- subject's self-assessment of disability (HAQ-DI) (CFB and percent CFB)
- Physician's Global Assessment of Disease Activity (CFB and percent CFB)

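### No analysis of the DAS28-hsCRP < 3.2 and < 2.6 proportions uses baseline DAS28-hsCRP; adding it to the supportive model is a cheap improvement of modest size

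*SAP*

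**What the plan says.** SAP Section 16, Table 12, treats the two threshold endpoints alike. The primary method is "Computation of response rate, point estimate and 2-sided 80% CI for Δ based on the" corrected Miettinen-Nurminen method, with no covariates. The supportive method is a "logistic regression with treatment and baseline hsCRP as covariate". Section 16.2.2 carries the ACR20 approach over to the < 3.2 and < 2.6 proportions, ending with "proportion, but without the sensitivity analysis". It also adds proportions by time point without imputation. Table 14 repeats the unadjusted interval in the hsCRP subgroups.

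The continuous version of the same score is handled differently. Section 16.2.1 states: "The ANCOVA will include baseline as a covariate and treatment group as an independent variable". Section 16.2.2 then says: "This analysis will also be applied to DAS28-hsCRP score CFB at Week 4 and Week 12". Table 12 lists an "ANCOVA model with baseline hsCRP as covariate" as a separate supportive analysis of the continuous score, so the main ANCOVA is best read as using baseline DAS28-hsCRP.

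The baseline score needs no new data. Section 13.3.1 says "Information on RA baseline disease characteristics collected during screening will be summarized in total and by treatment arm", and its list includes DAS28-hsCRP, both continuous and by category.

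**The concern.** ACR20, ACR50 and ACR70 measure percent improvement from the subject's own baseline. The DAS28-hsCRP thresholds are absolute end-states: a subject who starts near 4 needs a much smaller fall to pass 3.2 than one who starts above 6. The starting score is therefore the natural prognostic covariate for these two endpoints. The plan instead gives them the hsCRP model that it uses for the ACR endpoints.

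Two things are at stake. One is precision in the supportive analysis. The other is whether a chance difference between arms in starting disease activity, quite possible with about 30 subjects each, can be allowed for when these proportions are read.

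**Working it through.** **1. Inputs.** From Protocol 8.1 and SAP 7: about 60 mITT subjects randomized 1:1, so 30 per arm; 1-sided 10% level; ACR20 rates 0.46 and 0.21; stated power 80.2%; dropout 6.25%. From Protocol 5.3.1: hsCRP of at least 3.6 mg/L at entry. From Protocol 7.3.1.3 and SAP Appendix 2: the score is 0.56√TJC28 + 0.28√SJC28 + "0.014*GH + 0.36*ln(hsCRP+1) + 0.96". The documents give no threshold response rates, no DAS28-hsCRP spread and no correlations. All of these are assumed below.

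**2. The plan's own figure.** Enumerate two Binomial(30, p) arms and reject when d / √[p̄(1−p̄)(2/30)(60/59)] exceeds 1.2816. Power for 0.46 v 0.21 is 80.3%, against the stated 80.2%. Dropout: 60/(1 − 0.0625) = 64, as stated. No power is stated for the DAS28-hsCRP proportions.

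**3. Weight of hsCRP in the score.** The term is 0.36 × ln(4.6) = 0.55 at 3.6 mg/L and 0.36 × ln(41) = 1.34 at an illustrative 40 mg/L, a range of 0.79 points. For comparison, going from 6 to 28 joints moves the tender-joint term by 0.56 × (5.29 − 2.45) = 1.59 points and the swollen-joint term by 0.28 × (5.29 − 2.45) = 0.80. The global assessment can contribute up to 0.014 × 100 = 1.4. (The lower value of 6 is illustrative, because the entry minimum counts 66 or 68 joints.) Under assumed component spreads, the hsCRP term carries about 9% to 10% of baseline score variance, and raw hsCRP correlates 0.27 to 0.55 with the score.

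**4. Precision and chance imbalance.** Simulation with 30 per arm and 4,000 trials per setting. Assumed: Week 12 SD 1.2, placebo mean 4.5, effect −0.6, and correlation 0.33 between baseline DAS28-hsCRP and log hsCRP. Variances are for the risk difference, relative to unadjusted. One SE of imbalance is √(2/30) = 0.26 SD of the baseline score.

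| Correlation, baseline to Week 12 | 0.3 | 0.45 | 0.6 |
|---|---|---|---|
| < 3.2: variance, DAS28-hsCRP model | 0.98 | 0.92 | 0.82 |
| < 3.2: variance, hsCRP model | 1.02 | 1.01 | 0.99 |
| < 3.2: shift per 1-SE imbalance (points) | 2.1 | 3.1 | 4.3 |
| < 2.6: variance, DAS28-hsCRP model | 1.00 | 0.95 | 0.90 |
| < 2.6: variance, hsCRP model | 1.02 | 1.02 | 1.01 |
| < 2.6: shift per 1-SE imbalance (points) | 1.3 | 2.0 | 2.5 |

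In this set-up, power for < 3.2 was 51% to 53% unadjusted, 52% with hsCRP and 54% to 58% with DAS28-hsCRP.

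**5. Power under higher assumed rates.** Latent-probit outcome, 30 per arm, 2,500 trials per setting, 15% v 35%, correlation 0.4 between baseline hsCRP and DAS28-hsCRP, Firth-type logistic fit with a one-sided Wald test.

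| Correlation | M-N | hsCRP model | DAS28-hsCRP model | Gain over hsCRP | Gain over M-N |
|---|---|---|---|---|---|
| 0.3 | 68.1% | 66.4% | 67.4% | +1.0 | −0.7 |
| 0.5 | 67.5% | 66.4% | 70.6% | +4.2 | +3.1 |
| 0.7 | 70.3% | 70.5% | 78.6% | +8.1 | +8.3 |

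Null rejection for the logistic models was 8% to 10%. The simulation error of one power figure is about √(0.68 × 0.32/2500) = 0.9 points. At 10% v 27% the gains over the hsCRP model were 1.0, 2.8 and 8.2 points. A further run over both rate pairs gave about 1–2, 3.5–4 and 9–10 points. Taken together, the gain is about 1–2 points at 0.3, 3–4 at 0.5 and 8–10 at 0.7.

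**6. Few responders.** At 5% v 15% the expected count is 30 × 0.05 + 30 × 0.15 = 6. The DAS28-hsCRP logistic test had 44% to 51% power, against 52% to 54% for Miettinen-Nurminen, and was lower at every correlation. Part of that gap is size: null rejection was about 5% against about 12%.

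**The case against.** The strongest reply is that no decision rests on this. These are other secondary endpoints without multiplicity control, power is claimed only for ACR20, and the unadjusted interval remains valid under randomization. All of that stands, and it makes this an improvement rather than the correction of an error.

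Second, the SAP already covers much of the ground. The ANCOVA of the continuous score adjusts for its own baseline, baseline DAS28-hsCRP is tabulated by arm, and Section 16.2.2 plans shift tables by category from baseline to Week 12 with cut-offs at 2.6 and 3.2. A chance imbalance would therefore be visible. None of this gives a baseline-adjusted estimate for the two proportions.

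Third, hsCRP may be a deliberate choice. It recurs in the supportive models, the multiple imputation and the subgroups. Protocol 6.3 describes stratified randomization, but no factor is legible in the public text. If a factor tracks hsCRP or disease activity, dropping hsCRP could lose a design covariate, and imbalance would be smaller than simulated. This favours adding the baseline score over swapping it in.

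Fourth, the size depends on assumptions. Entry minimums narrow the baseline range, and counting subjects who discontinue as non-responders would weaken the link to baseline; the simulations in step 4 and step 5 include no dropouts. Against Miettinen-Nurminen at 10% v 27%, another 2,000-trial run gave 64.4% v 65.9%, 69.4% v 67.4% and 73.4% v 65.8% at correlations 0.3, 0.5 and 0.7, so the gain is clear only at the highest. This stands as a limit on the claim.

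**Conclusion.** The point holds as a modest improvement to a supportive analysis. No planned analysis of either proportion uses baseline DAS28-hsCRP, the SAP treats the continuous and binary readouts of one score differently without saying why, and the planned hsCRP model shows no material power gain over the unadjusted test. At about 30 per arm the gain for rates like 15% v 35% or 10% v 27% is negligible to large, depending on a correlation that the documents do not give.

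A reader might go further and infer one of the following, which the documents do not support:

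- **That the planned threshold analysis is biased or invalid.** Randomization protects the Miettinen-Nurminen interval; the imbalance issue is conditional on the baselines observed.
- **That the hsCRP model can do nothing about imbalance.** hsCRP is part of the score and is correlated with it.
- **That joint counts and the global assessment are known to carry most of the spread here.** No component variances are given; step 3 rests on assumed ones.
- **That a gain of 8 to 10 points should be expected, or that it extends to < 2.6.** The first needs a correlation of 0.7. With about 6 responders the adjusted test did worse than Miettinen-Nurminen.

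The ACR20 test and its stated 80.2% power are not touched.

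**What to change.** Amend SAP Table 12 before the codes are broken for the primary analysis, keeping Miettinen-Nurminen primary for both endpoints.

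- **< 3.2:** add baseline DAS28-hsCRP to the supportive logistic regression. Keep hsCRP only if it is needed, for example because it relates to a stratification factor. Report the standardised risk difference with its 80% CI beside the Miettinen-Nurminen interval. A prognostic covariate does not shrink the standard error of the log odds ratio, so the precision gain shows on the risk-difference scale. Name the variance method, such as the delta method or bootstrap.
- **< 2.6:** use baseline DAS28-hsCRP as the single baseline covariate with a penalised (Firth) fit. Label the result descriptive and claim no power gain.

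The covariate is already derived. The cost is a changed model statement plus a small amount of programming and validation for the standardised estimate and its variance, which the SAP does not yet specify.

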16.1 Primary Endpoint Analyses

The primary endpoint, ACR20 response rate at Week 12, will be presented on the mITT Analysis Set.

The ACR20 is a primary efficacy measure for which, at Week 12, a subject must have at least 20% improvement in the following ACR Core Set values.

- TJC (being the number of joints assessed as “Pain/Tender only” or “Pain/Tender and Swollen” among the 68 joint count) and
- SJC (being the sum of joints assessed as “Swollen only” or “Pain/Tender and Swollen” among the 66 joint count) and
- An improvement of at least 20% in at least 3 of the following 5 assessments:
 - Subject’s Global Assessment of Disease Activity
 - Subject’s Assessment of Pain

- Subject's Assessment of Physical Function as measured by the HAQ-DI
- Physician's Global Assessment of Disease Activity
- Acute phase reactant as measured by hsCRP.

In this trial, ACR20 response calculations will use the HAQ-DI for the subject's assessment of physical function and hsCRP as the measure of acute phase reactant.

Improvement of at least 20% of these assessments is defined as follows:

- TJC (68 joint count): a decrease of at least 20% of the number of tender joint compared to baseline
- SJC (66 joint count): a decrease of at least 20% of the number of swollen joint compared to baseline
- Subject's Global Assessment of Disease Activity: a decrease of at least 20% on the VAS compared to baseline.
- Subject's Assessment of Pain: a decrease of at least 20% on the VAS compared to baseline.
- Subject's Assessment of Physical Function: a decrease of at least 20% of the HAQ-DI score compared to baseline.
- Physician's Global Assessment of Disease Activity: a decrease of at least 20% on the VAS compared to baseline
- Acute phase reactant: a decrease of at least 20% of hsCRP measurement compared to baseline

The hypotheses tested are as follows:

- H0: Difference in ACR20 response rates at Week 12 (M2951 versus placebo) ≤ 0 .
- H1: Difference in ACR20 response rates at Week 12 (M2951 versus placebo) > 0 .

Tests will be based on the 2-sided 80% CI for Δ .

The Week 12 ACR20 proportion and a 2-sided 80% CI will be provided for each treatment group. The difference Δ in ACR20 proportions between M2951 + MTX and placebo + MTX, and a 2-sided 80% CI for Δ , based on the "corrected Miettinen-Nurminen" method (3) - method of Mee interval corrected with Miettinen and Nurminen factor $n/(n-1)$, n being the total number of evaluable randomized subjects - will be provided.

The 2-sided 80% CI for Δ based on the "corrected Miettinen-Nurminen" method will be computed with SAS® FREQ procedure, using RISKDIFF and CL=MN statements.

The primary analysis will be based on the mITT Analysis Set using post baseline LOCF for imputation of missing values for the ACR components. If a subject discontinued prior to Week 12, then the subject will be considered as ACR20 non-responder. The null hypothesis H0: $\Delta \leq 0$ will be rejected at the 1-sided 0.10 level if the lower limit of the 2-sided 80% CI exceeds zero.

The primary analysis will be repeated for subjects with baseline hsCRP ≥ 3.6 mg/L, as detailed in Table 14.

Additional sensitivity analyses will be performed on ACR20 response as described in Table 13.

